5. SELECTION OF PATIENT POPULATION

5.1 STUDY POPULATION

Up to 30 pediatric patients will be enrolled in this study, in up to 10 Clinical Centers in the United States.

Pediatric patients with a body weight (BW) greater than or equal to 15 kg receiving care in the Intensive Care Units of each participating hospital will be screened daily and identified for participation in the trial. See **Appendix E**, CRRT Management.

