6.3 BASELINE PERIOD

The Baseline Period begins at enrollment and ends at the start of the Observation Period. It is expected that the patient will begin the Observation Period before the patient has reached 12 hours of CRRT. The following information will be recorded as close to the start of the Observation Period as possible. Data from standard of care tests may be used as baseline data, as long as it is captured within the time frames noted.

- **Demographic Data**
 - a) Date of birth
 - b) Gender
 - c) Race/ethnicity
- **Hospitalization Data**
 - a) Hospital Admission Date
 - b) Hospital Admission Diagnosis
 - c) ICU Admission Date
 - d) ICU Admission Diagnosis
 - e) Medical History
- **Vital Signs/Physical Assessment (within 12 hours prior to the start of Observation Period unless otherwise indicated)**
 - Temperature
 - Blood Pressure, heart rate,
 - Body weight (within 24 hours if available)
 - PRISM II Score
 - Physical Exam
 - Urine Output (previous 24 hours)
 - ICU percent fluid overload at CRRT initiation (Defined as [(Fluid In (liters) – Fluid Out (liters))/ICU admission weight (kg)] x 100% where Fluid In and Fluid Out are calculated from ICU admission to CRRT initiation.
- **Clinical Laboratory Tests (within 12 hours prior to the start of Observation Period)**
 - CBC with differential
 - BUN/Creatinine
 - Na, K, Cl, HCO₃, Ca, Mg, Ionized Ca, PO₄
 - ALT, AST, Bilirubin, ALP, Total Protein, Albumin, Glucose
 - PT, PTT, INR
 - Urinalysis (if urine available)
- **Respiratory**
 - Status – Ventilator support (yes/no; date of intubation)
 - If on Vent: FiO₂
 - If on Vent with an arterial line: Arterial Blood Gas (12 hours prior to start of Observation Period)
 - If on Vent without an arterial line: Arterial Blood Gas (if available within 12 hours of start of Observation Period)
- **Blood for Research**
 - Blood sample will be sent to an outside laboratory for testing of biomarkers
- **Other (Event-driven)**
 - Acknowledgement (yes/no) to critical medications administered to the patient in the 24 hours prior to start of Observation Period
 - Adverse Events occurring since enrollment
 - Microbiology/culture data (within the last 72 hr.)

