10. DATA SAFETY MONITORING BOARD

An independent Data Safety Monitoring Board (DSMB) will review safety results over the course of the study on a schedule set by CytoPherx, Inc. and the DSMB. The DSMB will comply with the FDA Guidance: “Guidance for Clinical Trial Sponsors on the Establishment and Operation of Clinical Trial Data Monitoring Committees”. The DSMB will be formed to provide scientific and medical feedback for the study.

The DSMB will focus on the following areas:

- *Performance* – to assess study conduct and compliance;
- *Effectiveness* – to assess mortality and dialysis dependency;
- *Safety* – to assess the incidence, severity, relationship, and timing of adverse events and to identify safety concerns; and
- *Context* – to assess the study relative to the AKI literature.

The DSMB will reflect the disciplines and medical specialties necessary to interpret the data from the clinical study and to fully evaluate participant safety. The SCD-PED-01 DSMB will be made up of at least 2 medical practitioners with expertise in AKI and critical care medicine. The DSMB will operate under a charter and will identify prospective data display specifications to conduct independent data reviews. The DSMB will make recommendations to the Sponsor to continue the study as planned or to stop the study due to safety. The DSMB will meet to perform safety evaluations and to provide feedback to the Sponsor at least annually as well as after 5, 10 and 16 of the cohort has completed 60 day follow-up. An efficacy evaluation to historical controls will be accomplished after all 16 enrolled patients have completed 60 day follow-up. The DSMB reserves the right to request more frequent evaluations.

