Besides the test of the hypothesis the study is focused on observable, empirical and laboratory determinations of patient safety while on the SCD. Previous human trials have been conducted on the SCD device and the protocol contains a review of AE and SAE data from all SCD human studies and findings from those studies contributed to constructing the investigative safety profile. Safety endpoint measures specified in the protocol include adverse events, laboratory safety parameters, vital signs, ventilation status and hemodynamic variables. Device integrity and performance measurements are also defined as are circumstances which demand premature termination of SCD treatment.

Prolonged exposure to the SCD is anticipated to result in superior outcomes, although as noted above, this pilot study is not designed to assess for efficacy. However, we understand that a minimum amount of exposure to the SCD will be required for an appropriate safety analysis and for making any inference regarding efficacy. The ppCRRT experience demonstrated that the majority of patients (201/370) received CRRT for 1 to 7 days and exhibited 65% survival (Symons et al CJASN 2007 Table7). Assuming our trial includes patients with similar illness severity, we have established a 72 minimum number of hours a patient will be treated with the SCD to be included in the final outcome analysis.

This trial is an early safety efficacy study but is not powered for statistical significance. Insights into a comparison of historical controls matched to SCD treated patients will utilize the ppCRRT Registry to match for: etiology of AKI, co-morbidities, CRRT modality, dose and form of anticoagulant, adverse events. [10].

The ppCRRT Registry has data fields for the primary reason for CRRT, including AKI and its cause, as well as co-morbidities which will be matched for primary organ system involvement. The CRRT modality was evenly distributed between convective and diffusive modality, with 60% of the convective modalities provided as CVVH and 40% as CVVHDF. The anticoagulant protocol will be standardized with ACD-A/CaCl₂ and all centers used the same protocol in ppCRRT Registry as outlined in this study protocol. Thus, the ppCRRT Registry dataset will be able to be matched to our study patient cohort. Also as noted above, patients will be matched for age, size and PRISM II score.

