The Prospective Pediatric CRRT (ppCRRT) database will be used as a control for the CRRT treatment related factors including: patient age, gender, primary cause of AKI, total treatment duration, CRRT modality (CVVH, CVVHD, CVVHDF), CRRT small solute clearance (ml/1.73m²/hour), baseline estimated GFR (using the original Schwartz formula, which was used in the ppCRRT), urine output in the 24 hours prior to CRRT initiation (ml/kg/hour), percent fluid overload at CRRT initiation based on admission ICU weight, vasoactive medication number at time of CRRT initiation and mean airway pressure at CRRT initiation.

An additional analysis will also evaluate patients who have achieved targeted iCa levels during 90% of treatment time and those who do not.

In summary this protocol meets all criteria necessary for clinical scientific inquiry related to a test of hypothesis in a well monitored environment focused on patient safety during the conduct of the study. Basic statistics will be performed on the data sets along with historical data comparisons and subjected to subset analysis where appropriate. The results will help to guide the design of a future pivotal study of this device.

The rational for therapy, study objectives and endpoints, design, inclusion and exclusion criteria are explicitly defined. Patient safety parameters are well documented including safety reporting, safety observations and assays, procedures for patient withdrawal and study discontinuation criteria along with monitoring device integrity and performance. Lastly, a review of all prior SCD human study safety data is included in the protocol for full disclosure to study investigators and the informed consent document includes a full description of all known and potential risks of the device treatment.

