APPENDIX F – SCD-PED-01 Study Schedule of Events

	Baseline	Hr 0-24	Hr 25-48	Hr 49-72	Hr 73-96	Hr 97-120	Hr 121-144	Hr 145-168	Therapy End
Vital Signs/Physical Assessment									
Temperature , Body Weight (baseline only)	X	X	X	X	X	X	X	X	
Blood Pressure (if no bp, MAP acceptable), Heart Rate	X	X	X	X	X	X	X	X	
PRISM II Score	X								
Physical Exam	X								
Urine Output (previous 24 hours)	X	X	X	X	X	X	X	X	
Net Fluid Balance (previous 24 hours)		X	X	X	X	X	X	X	
Sepsis	X								
ICU Percent Fluid Overload at CRRT Initiation	X								
Clinical Laboratory Testing									
CBC with differential	X	q12h	q12h	q12h	q12h	q12h	q12h	q12h	
BUN/Creatinine	X	X	X	X	X	X	X	X	
Na, K, Cl, HCO ₃ , Ca, Mg, PO ₄ , Ionized Calcium	X	X	X	X	X	X	X	X	
ALT, AST, Bilirubin, ALP, TP, Albumin, Glucose	X	X	X	X	X	X	X	X	
PT, PTT, INR	X	X	X	X	X	X	X	X	
Urinalysis (if urine is available)	X								
Respiratory									
Arterial Blood Gas (pH, PaO ₂ , PaCO ₂) (if on vent)*	X	X	X	X	X	X	X	X	
Ventilator Settings (FiO ₂)	X	X	X	X	X	X	X	X	
Blood For Research									
Blood for Biomarkers	X		X(hr/48)		X(hr/96)		X(hr/144)		X
Extracorporeal Device Parameters									
CRRT (Settings- Event Driven)	X (hour 0)	X	X	X	X	X	X	X	
Post Filter Ionized Calcium	X (hour 0)	q1h until <0.40mmol/L; then q6h	q6h	q6h	q6h	q6h	q6h	q6h	
CRRT Device and SCD Performance (Event Driven)		X	X	X	X	X	X	X	
SCD 24hr. Daily Change		X	X	X	X	X	X	X	
Other (Event-Driven)									
Adverse Events	X	X	X	X	X	X	X	X	X
Critical Medications, Blood products (yes/no) per Appendix J	X	X	X	X	X	X	X	X	X
Diagnosis/Therapeutic Procedures	X	X	X	X	X	X	X	X	X
Microbiology/culture data	X	X	X	X	X	X	X	X	

*Required only if the presence of an A-line; see **Section 6.3** and **Section 6.4** for details

APPENDIX G – SCD-PED-01 Study Schedule of Events: Follow-up Period**Day 1 - 5 or until ICU discharge (whichever occurs first unless otherwise specified)**

Measurement	Hour 0 - 24	Hours 25 – 120 ¹
Vital Signs/Physical Assessment		
Blood pressure, temperature, and heart rate	X	X
Physical Exam	X	
Urine Output (from previous 24 hours)	X	X
Net Fluid Balance – (from previous 24 hours)	X	X
Clinical Laboratory Tests		
CBC with differential	X	
BUN/Creatinine	X	
Na, K, Cl, HCO ₃ , Ca, Mg, PO ₄ , Ionized Calcium	X	
Respiratory:		
Arterial Blood Gas (pH, PaO ₂ , PaCO ₂)	X	
Ventilator Settings (FiO ₂)	X	X
Other(event driven)		
Renal Replacement Therapy status	X	X
Microbiology/Culture Data	X	X
Adverse Events	X	X
Serious Adverse Event	X	X
Antibacterial Medications (yes/no)	X	X

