APPENDIX J – CRITICAL MEDICATION LIST

The following is a list of medication categories (with examples) to be acknowledged (yes/no) in the Case Report Forms if administered to the patient during the SCD-PED-01 Clinical Trial (starting at 24 hours prior to Observation until 168 hours of treatment or ICU discharge, whichever comes first. Only antibacterial use is captured during follow-up period.

ANTIBACTERIALS FOR SYSTEMIC USE

Ampicillin	Ceftazidime	Moxifloxacin
Azithromycin	Ciprofloxacin	Nafcillin
Aztreonam	Ciprofloxacin hydrochloride	Piperacillin
Bactrim (Sulfamethoxazole, Trimethoprim)	Clindamycin	Piperacillin w/tazobactam (Piperacillin, Tazobactam)
Cefadroxil	Daptomycin	Synercid (Dalfopristin,Quinupristin)
Cefalexin	Doripenem	Tigecycline
Cefazolin	Erythromycin	Tobramycin
Cefazolin sodium	Gentamicin	Vancomycin
Cefepime	Levofloxacin	
Cefepime hydrochloride	Linezolid	
Cefoxitin	Meropenem	
	Metronidazole	

ANTIMYCOTICS FOR SYSTEMIC USE

Amphotericin b, liposome	Fluconazole
Caspofungin	Micafungin

ANTITHROMBOTIC AGENTS

Acetylsalicylic acid	Clopidogrel	Enoxaparin sodium
Argatroban	Drotrecogin alfa	Heparin
Bivalirudin	Enoxaparin	Warfarin sodium

BLOOD SUBSTITUTES

Albumin	Albumin human	Blood, whole
Cryoprecipitate	Red blood cells	
Plasma	Red blood cells, leucocyte depleted	
Platelets		

VASOPRESSORS

Dobutamine	Norepinephrine	Phenylephrine hydrochloride
Dopamine	Norepinephrine bitartrate	Vasopressin
Epinephrine	Phenylephrine	
Milrinone		

APPENDIX K – CRRT PRESCRIPTION GUIDELINE and REGIONAL CITRATE ANTICOAGULATION (RCA) PROTOCOL EXAMPLE

1. **Purpose:** The purpose of the guidelines is to standardize, to the extent possible, the provision of CRRT to patients who require CRRT. While these guidelines should govern the CRRT prescription provided to most patients, there will be special circumstances (e.g. inborn errors of metabolism, exogenous toxin removal) that will require deviation from these guidelines.
2. **Modality:** CRRT will be prescribed as continuous veno-venous hemodiafiltration (CVVHDF). A total minimum small solute clearance of 2000 ml/min/1.73m² will be prescribed. The clearance will be divided equally between dialysis and hemofiltration as follows:
 - a. 50% as dialysis fluid using PrismaSateTM via the dialysis pump
 - b. 50% as replacement fluid divided between pre-replacement and post-replacement as follows:

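### The registry comparison names severity factors that the protocol's data lists do not collect, or time differently, and it fixes no short list of pre-treatment factors

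*Combined protocol and SAP*

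**What the plan says.** Section 11 describes the historical comparison in two places. The first says registry controls will be matched on cause of AKI, co-morbidities, CRRT modality, anticoagulant dose and form, and adverse events, and also on age, size and PRISM II. The second says the registry will be used as a control for eleven factors. Among these are total treatment duration, small solute clearance per 1.73 m², baseline eGFR by the original Schwartz formula, urine output in the 24 hours before CRRT initiation, percent fluid overload, and finally "vasoactive medication number at time of CRRT initiation and mean airway pressure at CRRT initiation". No algorithm, ratio, caliper, order of priority or missing-data rule is given.

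The data lists are narrower:

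- **Medications.** Section 6.3 asks for "Acknowledgement (yes/no) to critical medications administered to the patient in the 24 hours prior to start of Observation Period". Appendix J describes a "list of medication categories (with examples) to be acknowledged (yes/no) in the Case Report Forms".
- **Respiratory.** Section 6.3 asks for "Ventilator support (yes/no; date of intubation", with FiO2 and blood gas for ventilated patients. Appendix F lists FiO2 as the only ventilator setting.
- **Body size.** Appendix F has "Temperature , Body Weight (baseline only". Height is not listed.
- **Urine output.** Section 6.3 takes the previous 24 hours, recorded as close to the start of Observation as possible.

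On numbers, Section 5.1 states "Up to 30 pediatric patients will be enrolled in this study, in up to 10 Clinical Centers in the United States", while Section 10 states "An efficacy evaluation to historical controls will be accomplished after all 16 enrolled patients have completed 60 day follow-up".

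**The concern.** The study has one open-label arm, so any statement about mortality or dialysis dependency rests on how comparable the registry patients are. The number of vasoactive drugs and the mean airway pressure are the plan's own measures of circulatory and respiratory support when CRRT starts. If they are not recorded, they will drop out of the comparison by default. With no method stated, the choice of which remaining factors to use could be made after outcomes are known.

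The comparison is not peripheral. Section 3.1 puts it in the primary objective, the synopsis Evaluation Plan repeats it, Section 10 schedules it, and Section 11 says the results will inform a pivotal study.

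**Working it through.** **Step 1: count the factors.** The matched list has 9 items (6 + 3) and the control list has 11. Three appear in both (age, cause of AKI, modality), so 9 + 11 − 3 = 17 distinct factors. Adverse events and total treatment duration arise after treatment starts, which leaves 15. Some of these are treatment settings rather than patient characteristics.

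**Step 2: set the doubtful factors against the data lists.**

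| Factor in Section 11 | What the protocol requires | Result |
|---|---|---|
| Mean airway pressure at CRRT initiation | Ventilator yes/no, FiO2, blood gas | Not collected |
| Number of vasoactive drugs at CRRT initiation | Yes/no by category, 24 h before Observation | No count; different anchor |
| Urine output, 24 h before CRRT initiation | 24 h before Observation | Different anchor |
| Baseline eGFR; clearance per 1.73 m² | Weight, no height | Not derivable, assuming both need height |
| Percent fluid overload at CRRT initiation | Collected with that anchor | Available |
| PRISM II | Collected at baseline | Available |

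Size of the timing gap: Section 6.4 lets Observation start at any point before 12 hours on CRRT. In the extreme case nearly 12 of the 24 hours of urine collection, 12/24 = one half, fall after CRRT began. If CRRT and SCD start together, which Section 6.4 allows, the gap is zero.

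**Step 3: could all the factors be matched at once?** The plan gives no matching calculation to reproduce. The one registry figure that can be checked agrees with its description: 201/370 = 54.3%, a majority.

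Assumptions, none of them from the plan: exact matching, k independent binary factors each with prevalence p, and a pool of N = 370 (the denominator quoted in Section 11; the pool actually available is not stated).

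A patient with j factors present has a given profile with probability q = p^j (1 − p)^(k − j). The chance of at least one exact match is 1 − (1 − q)^N, averaged over j ~ Binomial(k, p).

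- k = 15, p = 0.5: q = 1/2^15 = 1/32,768. The chance is 0.0112, so 30 × 0.0112 = 0.3 patients matched.
- k = 15, p = 0.2: the chance is 0.3476, so 30 × 0.3476 = 10.4 patients matched.
- With 16 patients, the number in Section 10: 0.2 to 5.6 matched.
- With N = 201 and 30 patients: 0.2 to 7.8 matched.
- k = 10 (the control list without treatment duration), N = 370, 30 patients: 9.1 to 22.8 matched.

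**Step 4: events available for adjustment.** The 201 registry patients with 65% survival supply 201 × 0.35 = 70 deaths. At the same assumed mortality, 30 trial patients add 30 × 0.35 = 10.5. For 15 factors plus treatment, (70.35 + 10.5)/16 = about 5 deaths per parameter. The 201 are themselves selected on CRRT duration, and deaths among the other 169 registry patients are not stated.

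**The case against.** The strongest reply is that the plan never calls for a 15-way exact match. Section 11 uses matching language only for the first list. The missing factors are in the second, where the wording also allows regression adjustment or a description of balance. A reader might infer from 2^15 cells and 370/32,768 = 0.01 matches per patient that the comparison is impossible. The documents do not support that: the figure takes the least favourable prevalence and an exact match on everything. Taking only the matched list, without adverse events and without the form of anticoagulant (citrate for all trial patients under Appendix E), seven factors remain. On the same balanced binary assumption that gives 370/2^7 = 2.9 registry patients per trial patient. This stands, and the matching figures above describe only the extreme reading.

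A reader might also infer that severity goes uncontrolled. It does not: PRISM II covers oxygenation, blood pressure and coma score, and fluid overload is recorded at CRRT initiation. Whether the PRISM II time point differs from the registry's cannot be told, because the registry's is not given.

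The CRF is not in the documents and may hold more than the protocol requires, and Section 12 gives access to hospital charts. The height point depends on an assumption about the eGFR formula that the documents do not state. Finally, Section 11 says the study is not powered for statistical significance. That limits precision but does not remove confounding.

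None of this supplies the missing items. Adjustment needs airway pressure and a vasoactive count just as matching does.

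**Conclusion.** The point holds in a limited form. Two named factors, mean airway pressure and number of vasoactive agents, are not obtainable from protocol-required data. A third, urine output, is anchored to a different time by up to 12 hours. Two more, eGFR and clearance per 1.73 m², are not derivable if they need height. The comparison cannot use all of its stated factors as the protocol stands, but it can still be made by adjustment or propensity methods on the factors that are collected.

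Exact matching on all 15 remaining factors would leave most patients unmatched (0.3 to 10 of 30 matched, under the assumptions in the working). The plan does not commit to that method. What it lacks is any stated method and a defensible short list. Two listed factors should not be on such a list at all, because controlling for adverse events or total treatment duration conditions on what happens after treatment starts.

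This weakens the historical mortality and dialysis comparison. The description of safety in treated patients is not affected.

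**What to change.** 1. Add four items to Section 6.3 and Appendix F, taken from existing charts and anchored at CRRT initiation: mean airway pressure, count of vasoactive agents, height, and urine output in the prior 24 hours.
2. Before outcomes are reviewed, fix a short list of pre-treatment factors held in both the trial and the registry. Leave adverse events and total treatment duration off it.
3. Use that list in one prespecified adjusted or matched comparison, for example observed against registry-expected deaths with an interval. If matching is chosen, state the algorithm, ratio, caliper and balance check. The choice between a prognostic score and matching is partly preference; fixing it in advance is what matters.
4. State which patients enter the comparison: reconcile 16 with up to 30, and say how the rule "we have established a 72 minimum number of hours a patient will be treated with the SCD" applies, since a minimum exposure tends to exclude early deaths and the items above do not correct for that.

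The cost is a few CRF lines, some chart abstraction and a paragraph of analysis text. The downside is that fewer factors are controlled individually.
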